4.3.3. Assessment of efficacy after treatment

The efficacy of the treatment in participants will be determined 14-21 days post-treatment by collecting another two stool samples, which will be microscopically examined for STH using duplicate Kato-Katz thick smears, creating a total of four slides for this time point assessment. Participants will be considered hookworm cured if no eggs were found in the follow-up stool samples.

EPG will be assessed by adding up the egg counts from the quadruplicate Kato-Katz thick smears and multiplying this number by a factor of six. Geometric and arithmetic mean egg counts will be calculated for the two treatment arms before and after treatment to assess the corresponding ERRs. Individuals will not be included in the trial if the hookworm EPG < 100 (total of the four slides) and/or if there is only one Kato-Katz thick smear slide with a hookworm egg.

Once all follow-up samples have been analysed, all participants who were still found STH-positive will receive albendazole (400 mg single dose) and ivermectin (200 $\mu\text{g}/\text{kg}$), which is currently recommended against STH by the WHO's Essential Medicines List.

4.3.4. Treatment acceptability and age-appropriateness assessment

To compare the acceptability and age-appropriateness of each formulation two methods will be used: (1) an observer will fill in an observational sheet to record the participant's reaction to treatment (Appendix 3) (age-appropriateness), and (2) the participant him/herself (if aged 6 years or older) will respond to a brief questionnaire about the tablet he/she received (acceptability) (Appendix 3).

4.3.5. Caregiver knowledge assessment

In this clinical trial we will embed a parallel study focused on (1) assessing whether caregivers understand the content of the study (and its ICF) and (2) exploring different methods of transmitting the information we intend caregivers to understand before deciding whether their child should participate in our clinical trial and comparing their performance. Caregivers who show up will be randomly assigned to one of four groups with different types of information interventions: (i) no information, (ii) oral information session, (iii) information session with slideshow, and (iv) oral information session plus a theatre. The theatre will be performed by members of the local community with guidance of the research staff regarding its content. Caregivers' understanding will be measured using a short questionnaire which will be pre-tested in a local community (Appendix 5). This questionnaire also includes asset socioeconomic questions.

Interviewers will receive specific training. Caregivers assigned to the control group (no information group) will not have attended any of the three types of information sessions by the time they respond to the questionnaire. However, before they are invited to sign the ICF, they will have to attend an information session with slideshow.

4.4. Measure to minimize bias

Study participants eligible for treatment will be randomly assigned to one of the two treatment arms using a computer-generated stratified block randomization code. The random allocation sequence with varying random blocks of four or eight and stratified by 2 levels of baseline infection intensity (light: 1-1999 EPG, and moderate plus heavy: ≥ 2000 EPG hookworm infections) will be provided by a statistician. Both treatment arms will have an equal number of participants with light infection intensity, although the number of light *versus* moderate/heavy infections are not expected to be equal within each arm, depending on the distribution of infection intensity in the recruited cohort.

4.5. Study duration

The trial is estimated to last 12 weeks with each participant’s involvement lasting up to 10 weeks. The screening for the baseline will start about five weeks prior to the treatment. Follow-up screening will take place 14-21 days post-treatment. Schedules of visits are summarized below.

4.6. Schedule of visits

Table 1 briefly presents the distribution of tasks along the trial.

Table 1. Schedule of visits during treatment period.

	Baseline	Examination/Treatment/Safety			Follow-up	
	Days -35 to -1/0	0	Hours 3	24	Days 14 to 21	Days 22 to 29
Sample collection and diagnosis	X				X	
Informed consent	X					
Caregiver questionnaires	X					
Demographics	X					
Medical History		X				
Physical and clinical examination		X				
Hb level and pregnancy assessment		X				
Randomization and treatment		X				

Capturing AEs/ SAEs	X	X	X*
Administration of ALB+IVM (if still infected at follow-up)			X
Observational sheet	X		

* Passive collection of AEs/SAEs (only when a child/caregiver contacts a staff member).

5. Selection of the trial subjects

5.1. Recruitment

The study will be carried out in preschool- and school-aged children (age: 3-12 years) in **five** primary schools with kindergarten (Wawi, Mvumoni, Bwagamoyo, Piki **and Mzambarauni**) on Pemba, Tanzania, a hookworm endemic area [20-22, 26, 27]. The study will be school-based. Caregivers of potential participants will be invited to participate in an information session where the research staff will explain the purpose and procedures of the study, as well as potential benefits and risks of participating. Particular emphasis will be given to the fact that caregivers should oversee the sample collection to avoid sample mix ups. Caregivers will be encouraged to ask questions in an open discussion forum.

Caregivers interested in having their child/children participate in the study will be invited to complete the process of informed consent by signing the informed consent form (ICF) (Appendix 1). See section 10.3 for further details on obtaining informed consent. Only participants who have written informed consent will be assessed for study eligibility criteria during screening procedures.

5.2. Inclusion criteria

- Male or female children aged between 3 and 12 years;
- Written informed consent signed by caregiver;
- Was examined by a study physician before treatment;
- Provided two stool samples at baseline;
- Hookworm EPG ≥ 50 and at least two Kato-Katz thick smears slides with more than one hookworm egg;

5.3. Exclusion criteria

- Pregnant;
- Presence or history of major systemic or chronic illnesses, as assessed by a medical doctor, such as can upon initial clinical assessment;
- Suffers from severe anemia (Hb < 80 g/l);
- Received anthelmintic treatment or metronidazole within past four weeks.
- Attending other clinical trials during the study.

Participants who were diagnosed with hookworm, *A. lumbricoides* and/or *T. trichiura* but were excluded from the clinical trial due to one or several of the above-mentioned exclusion criteria, including withdrawals, will be offered standard anthelmintic treatment (combination of albendazole and ivermectin), except for pregnant girls. In the presence of major systemic or chronic illnesses, besides providing the standard anthelmintic treatment, we will facilitate the best locally available care and/or support.

5.4. Criteria for discontinuation of trial

A subject can be discontinued from the study for the following reasons:

- Withdraws from the study (this can happen anytime as participation is voluntary and there are no further obligations once a participant withdraws); data obtained prior to the withdrawal will be included in the analysis to ensure the validity of the trial. Data of withdrawn participants are fully anonymised once analysis is complete.
- At the discretion of the PI or co-PI, if the participant is not compliant to the requirements of the protocol.

Discontinued subjects will not be replaced. If, for any reason, a subject is discontinued from the study before the end of treatment evaluations, the adverse event (AE) assessment will still be conducted.

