The overall goal of this study is to determine if a chewable formulation of mebendazole is superior to a swallowable formulation tablet of mebendazole (standard of care) against hookworm in children.

We hypothesize that the chewable formulation of mebendazole has a higher efficacy against hookworm infections than the swallowable one. Better absorption and bioavailability as well as better palatability are expected to contribute to superior efficacy.

The **primary objective** of the study is to compare the egg reduction rates (ERRs) of two different mebendazole formulations against hookworm in children (3 - 12 years old): (i) 500 mg of a single chewable mebendazole tablet and (ii) 500 mg of a single solid mebendazole tablet.

The **secondary objectives** of the trial are:

- To evaluate the safety and tolerability of the two formulations
- To evaluate the CR of the two formulations against hookworm
- To determine the CRs and ERRs against *Ascaris lumbricoides* and *Trichuris trichiura*
- To investigate the acceptability and age-appropriateness of both formulation when administered to children between 3 and 12 years of age

The **exploratory objectives** of this study are:

- To assess how well caregivers understand the clinical trials aim, procedures, their rights, risks and potential benefits

- To compare the effect of different methods of providing information on their understanding of the clinical trial

4. Methodology

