4.2. Type of trial

Randomized controlled, open-label, parallel-group, superiority, phase 2 trial.

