8.3. Description of statistical methods

The primary analysis will use the full analysis set (available case population) according to the intention to treat principle defined as all randomized subjects which provide any follow-up data. Only subjects which were negative at baseline and erroneously randomized will be excluded from the analysis. Palatability and ease of swallowing are critical attributes in children; therefore, a per-protocol analysis will be conducted additionally to disentangle drug efficacy from adherence effects.

Geometric mean egg counts will be calculated for the different treatment arms before and after treatment to assess the corresponding ERRs. The ERR will be calculated as:

$$ERR = 1 - \frac{\frac{1}{n} e^{\sum \log(EPG_{follow-up} + 1)} - 1}{\frac{1}{n} e^{\sum \log(EPG_{baseline} + 1)} - 1}$$

Bootstrap resampling with 5,000 replicates will be used to calculate 95% confidence intervals (CIs) for ERRs and the difference between the two ERRs. Superiority will be claimed if the 95% confidence interval of the difference in ERRs does not include unity (primary hypothesis).

Differences in CRs will be assessed using unadjusted logistic regressions. In a subsequent analysis an adjusted logistic regression (adjustment for age, sex, weight and strata) will be performed.

AEs will be evaluated descriptively as the difference of proportion reporting AEs before and after treatment.

9. Duties of the investigator

The investigators are responsible for an adequate data quality. Prior to the initiation of the study, a short investigator's meeting will be held with the investigators and their study coordinators and a member from Swiss TPH. This meeting will include a detailed discussion of the protocol, performance of study procedures (SOPs from previous studies available on site), CRF completion, and specimen collection and diagnostic methods.

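### Discretionary discontinuation for non-compliance, by investigators who know the arm, can take poor tablet-takers out of the primary egg-reduction analysis, because Section 5.4 does not require their follow-up stools

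*Combined protocol and SAP*

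**What the plan says.** - **Who may be discontinued (Section 5.4).** Besides voluntary withdrawal, a child may be taken out of the study "At the discretion of the PI or co-PI, if the participant is not compliant to the requirements of the protocol". Non-compliance is not defined, and the decision need not be made blind to arm. Discontinued children are not replaced.
- **What happens next (Section 5.4).** After any discontinuation, "the adverse event (AE) assessment will still be conducted". The follow-up stools are not mentioned. For voluntary withdrawal, "data obtained prior to the withdrawal will be included in the analysis to ensure the validity of the trial"; no matching statement covers discontinuation for non-compliance.
- **Who knows the arm.** Section 4.2 describes the trial as "Randomized controlled, open-label, parallel-group, superiority, phase 2 trial". The Synopsis blinds outcome assessors only. Under Section 5.5 a co-PI gives the tablet and records the child's reaction.
- **Primary analysis set (Section 8.3).** Under the intention-to-treat principle it is "all randomized subjects which provide any follow-up data". One exclusion is listed: "Only subjects which were negative at baseline and erroneously randomized will be excluded from the analysis".
- **Adherence (Section 8.3).** It has its own analysis: "a per-protocol analysis will be conducted additionally to disentangle drug efficacy from adherence effects".
- **Hypothesis (Section 3).** "Better absorption and bioavailability as well as better palatability are expected to contribute to superior efficacy".

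**The concern.** Section 8.3 implies that children who take the tablet badly belong in the primary comparison and are set aside only in the per-protocol analysis. Section 5.4 opens a way out of the primary comparison before the outcome is measured. The way out is discretionary, the people using it know the arm, and the trigger may be linked to the formulation itself. If refusal or spitting out is commoner with one tablet, the losses will differ between arms, and the children lost will tend to be those with little egg reduction. An available-case analysis does not correct for that. At stake is whether the primary ERR difference reflects the formulations as given to all randomised children, or partly reflects who was kept in follow-up.

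**Working it through.** **1. How a child is lost.** Three things must happen: the child is judged non-compliant, the PI or co-PI chooses to discontinue, and no day 14-21 stool is then collected. Section 5.4 permits the first two and is silent on the third. Without a follow-up stool there is no follow-up EPG. Even if adverse event data counted as follow-up data under Section 8.3, the ERR formula could not use the child.

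**2. The plan's own figures (Section 8.2).** ERRs of 38% and 64% (difference 26 points), 160 per arm for 80% power, 200 per arm after allowing 10% loss and a 14% margin. The inflation reproduces: 160 × 1.10 × 1.14 = 200.6; 160 × 1.24 = 198.4; (160 / 0.90) × 1.14 = 202.7. The 160 comes from resampling data that are not in the documents, so it cannot be checked here.

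**3. Assumptions for the size of the bias.** The documents give no rate of non-compliance or discontinuation, so I take 2%, 5% and 10% of one arm. I also assume that removed children have no egg reduction, that baseline geometric means are equal, that a normal approximation holds on the log scale (ignoring the +1 offset), that 180 per arm are evaluable (200 × 0.90), and that the 95% interval acts as a two-sided 5% test of no difference.

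The log-scale SD is solved back from the plan's figures. The log difference is ln(0.62 / 0.36) = 0.544, so SD = √(160/2) × 0.544 / (1.960 + 0.842) = 1.74.

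**4. Formula.** If a fraction q with no reduction is removed from an arm whose true ERR is E, the ERR in those left is 1 − (1 − E)^(1/(1 − q)). For q = 0.10, swallowable: 1 − 0.62^(1/0.9) = 41.2%, difference 64 − 41.2 = 22.8 points. Chewable: 1 − 0.36^(1/0.9) = 67.9%, difference 67.9 − 38 = 29.9 points.

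**5. Results.** With no removal, the difference is 26.0 points and power is 84%.

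| Removed from one arm (of 200) | Swallowable only: difference, power | Chewable only: difference, power | Equal true ERRs of 38%: spurious difference, rejection rate |
|---|---|---|---|
| 2% (4) | 25.4 points, 83% | 26.7 points, 87% | 0.6 points, 5.0% |
| 5% (10) | 24.5 points, 80% | 27.9 points, 90% | 1.5 points, 5.2% |
| 10% (20) | 22.8 points, 74% | 29.9 points, 94% | 3.2 points, 5.9% |

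**6. Check on direction from the other side.** Suppose instead that 38% and 64% hold only in children who ingest the tablet. The ERR in all randomised children is then 1 − exp[(1 − q) × ln(1 − E)]. With assumed non-ingestion of 10% (swallowable) and 2% (chewable), the ERRs are 35.0% and 63.3%, a difference of 28.3 points, against 26 if these children are dropped. With 20% and 2% the difference is 31.5. With 2% and 10% it is 22.7. The directions agree with step 5: losing poor takers from the swallowable arm shrinks the difference, and losing them from the chewable arm inflates it.

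**The case against.** A reader might infer that Section 5.4 takes non-compliant children out of the intention-to-treat set as a matter of rule. The documents do not say that. Section 8.3 lists only baseline-negative children randomised in error as excluded, and a discontinued child who still gives stool is analysed. Stool collection after discontinuation is not required, but neither is it forbidden. This objection stands and limits the point to what can happen.

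A reader might also infer that the children at risk of removal are the ones in whom the formulations are expected to differ. That goes too far. Section 3 also names absorption and bioavailability, which act in children who do ingest the tablet.

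Non-compliance in Section 5.4 is generic and could equally mean taking a forbidden drug; nothing links it expressly to tablet refusal. Opportunity is limited too. Sections 5.5 describes one supervised dose with ingestion confirmed, crushing or added water for younger children, three hours of observation and re-dosing after early vomiting. Numbers are therefore probably small. Finally, if the chewable tablet is the more palatable, losses would fall mainly in the swallowable arm and work against a superiority claim.

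All of this reduces the likely size. None of it closes the gap: the term is undefined, the decision is unblinded, and follow-up stools are not secured.

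**Conclusion.** The point holds as a possibility that the wording leaves open. Following Section 5.4 can produce exclusions related to arm and outcome in an analysis that Section 8.3 describes as intention to treat. To say that the primary analysis thereby becomes a per-protocol analysis would be too strong, since removal is neither automatic nor likely to be frequent.

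The bias can go either way and is probably small: roughly 3 points down to 4 points up on a 26-point difference at 10% one-arm removal, and less at 2-5%. The false-positive rate stays at or below about 5.9%. Power could fall from 84% to about 74% if 10% of the swallowable arm were lost. These figures rest on assumed removal rates and on no egg reduction in those removed; they show scale and are not predictions. The change is worth making because it is cheap and brings Section 5.4 into line with Section 8.3.

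**What to change.** In Section 5.4:

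- Do not end follow-up for non-compliance. Say what counts as non-compliance and record it as a protocol deviation.
- Seek both day 14-21 stools from every randomised child unless consent is withdrawn.

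In Section 8.3:

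- State that these children stay in the primary analysis in the arm to which they were randomised, and are excluded only from the per-protocol analysis.
- Report discontinuations by arm, with reasons.

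One further matter has to be settled for the stools to be interpretable. Section 5.3 offers albendazole plus ivermectin to infected children excluded from the trial and extends this to withdrawals, while Section 4.3.3 and Table 1 place that treatment after the follow-up samples. Section 5.4 does not say whether or when it reaches children discontinued for non-compliance. If it came before the stools, the counts would no longer reflect the randomised tablet. Sections 5.3 and 5.4 must be reconciled on this, and any such treatment given before the stools should be recorded. Which clinical rule applies is for the investigators to decide.

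The cost is protocol wording, that reconciliation, and a few stool samples at a visit already scheduled.

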5.5. Treatment of subjects

Both mebendazole tablet formulations will be donated by the WHO. Tablets will be kept in their original packing until they are administered to participants. However, we will cut the sheet of encapsulated tablets so that we have them individualized but still in the capsule. To ensure the treatment allocation is concealed, prior to the trial initiation, two subjects independent to the study will prepare sealed, opaque and sequentially numbered envelopes containing the correct encapsulated tablet (chewable or swallowable) for each participant.

On treatment day, one 500 mg tablet will be orally administered to each participant. However, the mode of administration will depend on (i) whether the child is 3-5 year old or 6-12 year old and (ii) on the treatment arm he/she has been allocated to:

- **3-5 year olds** allocated to the **swallowable tablet** arm will be given the crushed tablet on a spoon mixed with a small amount of clean water;
- **6-12 year olds** allocated to the **swallowable tablet** arm will be given the whole tablet to swallow with a glass of clean water;
- **3-5 year olds** allocated to the **chewable tablet** arm will be encouraged to chew the tablet and swallow it without water; if they cannot chew it then a small amount of water will be added to the tablet in a spoon;
- **6-12 year olds** allocated to the **chewable tablet** arm will be encouraged to chew the tablet and then swallow it without water.

The staff administering treatment will be trained in case any child chokes. Treatment arm, date and time will be recorded in the case report form (CRF) (Appendix 2). All drugs will be administered in the presence of at least one study investigator, and ingestion confirmed. The individual observational sheet will be filled out by the co-PI administering the drugs during the treatment of each participant, and as soon as the participant is done with treatment one staff member will pose him/her questions concerning the tablet to explore the acceptability (Appendix 3). This questionnaire will only be administered to the participant if he/she is aged between 6-12 years.

Subjects will be asked not to take any drugs other than those prescribed by the study medical team until they have provided the two follow-up stool samples. After ingestion of the medication, which will be done at school, the subjects will be observed for 3 hours to ensure retention of the drug. Vomiting within one hour post-dosing will require re-dosing. The subjects will not be allowed more than one repeated dose. No re-administration will be needed for subjects vomiting after one hour. The site co-PI is responsible for drug accountability at the study site. Maintaining drug accountability includes careful and systematic study drug storage, handling, dispensing and documentation of administration. Any study product that is unused at the conclusion of the study will be destroyed.

5.6. Concomitant therapy

All medications taken one month before and during the study period until the last stool examination between day 14 and 21 (follow-up) must be recorded with indication, dose regimen, date and time of administration.

Medication(s)/treatment(s) permitted during the trial:

- Analgesics and antipyretics are allowed to be given to the subjects in case of fever, antiemetics to prevent nausea and vomiting and/or antibiotics to prevent or treat bacterial superinfection.

Medication(s)/treatment(s) NOT permitted during the trial:

- No other active drugs against helminths are permitted during the trial.
- Metronidazole.

6. Safety assessments

Few AEs have been reported following mebendazole administration. The most common reported AEs are abdominal cramps, headache, diarrhoea, fever and fatigue [22, 28, 29]. The chewable mebendazole has previously caused convulsions but only in infants below the age of one year which are not included in this study. The concomitant administration of the chewable mebendazole and metronidazole has caused neutropenia and agranulocytosis [30]. The safety profile of mebendazole will be assessed through the recording, reporting and analysis of baseline medical conditions, a physical examination and active questioning at 3 and 24 hours post-treatment (see section 6.2).

